6.6.3 ECG Results

Summaries of ECG parameters and findings are the same as specified in the M-SAP.

6.6.4 Vital Signs and Weight

Summaries and analyses of vital signs and weight are the same as specified in the M-SAP.

6.6.5 Suicidality

Summaries of suicidality are the same as specified in the M-SAP.

6.7 Other Analyses

6.7.1 Participant Disposition

All participants consented to the Master Protocol between the time of the first and last consent of a participant assigned to a regimen included in the FAS will be summarized as a single set for the following events: consented to the Master Protocol, failed screening for the Master Protocol, other reasons not assigned to a regimen (including timing out of the screening window, death, withdrawal of consent, early termination, and administrative termination), and assigned to a regimen. Reasons for Master Protocol screen failure will be summarized.

All participants in the above sample assigned to a regimen will be summarized as two sets (final screening for RGE vs. final screening for a non-RGE contributing regimen) for the following events: consented to a regimen, failed screening for a regimen, other reasons not randomized within a regimen (including timing out of the screening window, death, withdrawal of consent, early termination, and administrative termination), and randomized within a regimen. If a given individual is screened multiple times prior to randomization within a regimen, then the final screening experience of that individual will be summarized. Reasons for RGE screen failure will be summarized separately for all participants screened for RGE whether that was their final screening experience or not.

Page 34 of 37

All participants in the FAS will be summarized as two sets (randomization to active study drug vs. randomization to placebo) for the following events: initiated regimen-specific study drug, prematurely terminated study participation due to death, withdrawal of consent, early termination, loss to follow-up, or administrative termination, completed 24-week follow up, and completed a safety follow-up visit vs. continued into the OLE. Reasons for withdrawal of consent or early termination after randomization will be summarized.

6.7.2 Study Drug Compliance and Tolerance

Summaries of study drug compliance and tolerance are the same as specified in the M-SAP with the clarification that summaries will be reported for the ERO and SRO analysis sets and that date of permanent discontinuation of study drug is the date of last use of double-blind study drug among all participants in a given analysis set. The number of days of exposure to study drug will be calculated as the number of days from dose initiation to drug withdrawal, inclusive, less any day(s) during which use of study drug was interrupted. The proportion of participants who interrupted study drug or reduced study drug dosage and the time to first study drug interruption or dosage reduction will be summarized. The number of days of exposure to a reduced dosage of study drug will be summarized.

6.7.3 Concomitant Medication Use

Summaries of concomitant medication use are the same as specified in the M-SAP with the clarification that medications taken at baseline and those initiated after first dose of study drug that were not taken at baseline will be separately summarized and will be classified by ATC Therapeutic class and WHODrug Preferred base name.

Time to post-baseline initiation of edaravone, riluzole, or sodium phenylbutyrate/taurursodiol individually and in combination will be summarized by Kaplan-Meier product-limit estimates among the subset of participants who were not on a given drug or combination of drugs at baseline.

6.7.4 Medical History

Medical histories will be summarized by MedDRA system organ class, high level term, and preferred term in the STF and SRO analysis sets.

6.7.5 Blindedness

The proportions of participants and site investigators who report on the Exit Questionnaire a guess of active vs. placebo treatment assignment, each level of surety of that guess, and each of five pre-specified reasons for making a treatment assignment will be summarized by treatment group in the FAS and ERO. Treatment-dependent differences in the proportion guessing active treatment assignment will be tested among all respondents and among those stating they are at least somewhat sure of their guess by Fisher's exact test and the difference in proportion guessing active treatment assignment will be estimated with confidence bounds.

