#### **Number of Planned Participants and Treatment Groups**

The number of planned participants for this regimen is approximately 160.

There are 2 treatment groups for this regimen, active and placebo. Participants will be randomized in a 3:1 ratio to active treatment or placebo (i.e., 120 active: 40 placebo).

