6.1 Analysis Sets

The ITT analysis set is henceforth referred to as the Full Analysis Set (FAS) and defined as follows:

 Full Analysis Set (FAS): Participants who were randomized within RGE plus placebo participants from regimens A-D who had an opportunity to complete placebo-controlled follow-up, classified according to their randomized treatment assignment. Participants who discontinue study drug but remain in the study will be included in the FAS. Observations completed after regimen data lock are excluded. Participants determined to not meet ALS diagnostic criteria are excluded.

The definition of the STF analysis set is revised as follows:

• Safety Full (STF) Set: Participants who initiated treatment within RGE plus placebo participants from regimens A-D who are not known to be ineligible for RGE and who initiated treatment in their respective regimen, classified according to the treatment they actually received. Observations made after premature permanent discontinuation of study drug are included in this sample, should such participants remain on study. Observations completed after regimen data lock are excluded.

An analysis set restricting shared placebo participants to those regimens in which study drug is administered by the same route as RGE is defined as follows:

• Efficacy Common Mode of Administration (ECM) Set: The subset of participants in the FAS who are in regimens in which study drug is administered by the same route as RGE.

The definitions of the ECC, ERO, STN, and SRO analysis sets are the same as described in the M-SAP with reference to the ITT analysis set now referencing the FAS analysis set.

• Efficacy Per-protocol (EPP) Set: The subset of participants in the FAS analysis set who initiated study treatment and who were not involved in protocol deviations related to eligibility, treatment, follow-up, assessment, or use of other disease-modifying treatments for ALS, classified according to the treatment they actually received. Final specification of participants included vs. excluded from the EPP analysis set will be defined prior to data lock. Inclusion or exclusion from the EPP analysis set of any participant for whom treatment

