assignment was unblinded prior to data lock will be governed by the prespecified criteria above. If a participant's data are truncated for inclusion in the EPP analysis set due to a time-dependent event (e.g., non-adherence to protocol-specified dosing, initiation of a prohibited medication, initiation of edaravone, riluzole, or sodium phenylbutyrate/taurursodiol), clinical events observed up to 28 days after the censoring event will be included in the EPP analysis set. Data from placebo participants shared from other regimens will not be truncated due to non-adherence to protocol-specified dosing.

An analysis set that excludes participants who used sodium phenylbutyrate/taurursodiol during their follow-up for the placebo-controlled period is defined as follows:

• Efficacy Relyvrio Free (ERF) Set: The subset of participants in the ERO who were not using sodium phenylbutyrate/taurursodiol at baseline and did not start using sodium phenylbutyrate/taurursodiol after baseline and prior to completion of their Week 24 visit or death, earlier termination, withdrawal, or loss to follow-up prior to the end of the Week 24 visit window if they did not complete a Week 24 visit.

Applicable analysis sets (FAS, ECC, EPP, and STF) will include shared placebo participants from regimens A, B, C, and D. As RGE is the only regimen among the contributing regimens that is administered as an IV infusion, the ERO and ECM analysis sets are synonymous and only the ERO analysis set will be referenced. Similarly, the SRO and STN analysis sets are synonymous and only the SRO analysis set will be referenced.

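### The blinding test in SAP 6.7.5 is, on its natural reading, also run in the FAS, where trehalose is compared partly with non-IV placebo; only the ERO comparison tests the trehalose blind

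*SAP*

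**What the plan says.** SAP section 6.7.5 (Blindedness) covers guesses of treatment assignment given on the Exit Questionnaire by participants and by site investigators. The guesses, how sure respondents are, and their reasons "will be summarized by treatment group in the FAS and ERO". The next sentence specifies the inference: "Treatment-dependent differences in the proportion guessing active treatment assignment will be tested among all respondents". The method is Fisher's exact test, repeated in the respondents who are at least somewhat sure, and a difference in proportions is given with confidence bounds. The sentence names no analysis set and does not say whether participants and investigators are tested separately. The section gives no significance level, no decision rule, and no statement of which set's result is the assessment of the trehalose blind.

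SAP section 6.1 defines the FAS as "Participants who were randomized within RGE plus placebo participants from regimens A-D who had an opportunity to complete placebo-controlled follow-up". The same section defines a common-route set as "The subset of participants in the FAS who are in regimens in which study drug is administered by the same route as RGE", and then notes that "RGE is the only regimen among the contributing regimens that is administered as an IV infusion, the ERO and ECM analysis sets are synonymous". Two things follow. The ERO contains only participants of the trehalose regimen (RGE), that is, trehalose versus saline infusion. And every shared placebo participant in the FAS received placebo by a route other than IV infusion.

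**The concern.** A test of blinding asks whether people on active treatment and people on its matching placebo differ in what they believe they received. That needs both groups to have been exposed to the same blind. In the FAS, the active group's guesses concern a weekly trehalose infusion against a saline infusion. The shared-placebo guesses were formed under other regimens, with other products and another mode of administration. Arm and regimen are confounded, and Fisher's test has no term that could separate them. A difference, or its absence, can come from how people in regimens A-D guess and not from the trehalose blind.

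Other parts of the plan sharpen the contrast:

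- Protocol section 9.3 justifies sharing controls by expecting no systematic difference in the primary endpoint. It says nothing about treatment guesses.
- The adjusted CAFS analyses and the repeated-measures model (SAP 6.5.2 and 6.5.3) carry a regimen effect. The blinding test does not.
- Pharmacokinetics and CSF LC3-II (SAP 6.5.13 and 6.5.14) and compliance and tolerance (SAP 6.7.2) are reported in regimen-only sets.

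The primary outcome is a rated scale, so readers may use the blinding result when they weigh the primary result. Two p-values for one question could disagree, and the SAP does not say which to use.

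**Working it through.** **Inputs from the documents.** RGE randomizes about 160 participants 3:1 (Protocol, Number of Planned Participants and Treatment Groups). 160 × 3/4 = 120 active and 160 × 1/4 = 40 placebo, which matches the stated split. The documents give no planned size, power or expected guess rate for the blinding test, so there is no further figure to reproduce.

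**Assumptions, none of them in the documents.** Shared placebo S = 80, 120 or 160 (160 would be four regimens of 40); everyone responds; two-sided Fisher's exact test at 0.05; guess rates as shown below.

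**Share of FAS placebo from other regimens:** S/(S + 40) = 80/120 = 67%, 120/160 = 75%, 160/200 = 80%. It exceeds half whenever S is above 40.

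**Expected rate of guessing active in the pooled placebo group:** (40 × p_RGE + S × p_shared)/(40 + S). At S = 160:

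- Intact blind, p_RGE = 60%, p_shared = 45%: (24 + 72)/200 = 48%. The true gap within the regimen is 0 points; the FAS shows 60 − 48 = 12.
- Broken blind, active 65%, p_RGE = 35%, p_shared = 65%: (14 + 104)/200 = 59%. The true gap is 30 points; the FAS shows 65 − 59 = 6.

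**Rejection probability.** For each design, the exact probability is summed over all binomial outcomes for which Fisher's test gives p ≤ 0.05. The ERO compares 120 with 40; the FAS compares 120 with 40 + S.

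(a) RGE blind intact: 60% guess active in both RGE arms. The ERO rejects in 4.0%.

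| Shared placebo guessing active | FAS, S = 80 | FAS, S = 120 | FAS, S = 160 |
|---|---|---|---|
| 60% (same as RGE placebo) | 3.9% | 4.4% | 4.5% |
| 50% | 14.7% | 21.2% | 27.9% |
| 45% | 29.0% | 42.7% | 54.0% |
| 40% | 48.1% | 67.1% | 78.6% |

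(b) RGE blind broken: 65% of active and 35% of RGE placebo guess active. The ERO detects this in 90.1%.

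| Shared placebo guessing active | FAS, S = 80 | FAS, S = 160 |
|---|---|---|
| 60% | 51.0% | 41.2% |
| 65% | 31.1% | 17.2% |

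(c) The benign case. If shared placebo guess as RGE placebo do, the intact-blind rejection rate stays at 3.9% to 4.5% (first row of (a)). For a broken blind at 70% versus 45%, FAS power is 97.0% to 99.3%, against 76.5% in the ERO.

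**Sensitivity to response.** With 80% responding, case (a) at 45% gives 23.7%, 35.9% and 42.2% for the three values of S, against 3.8% in the ERO. The pattern is the same.

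**The case against.** The strongest reply is that the valid comparison is already planned. Section 6.7.5 names the ERO, which holds only RGE participants, so a disagreement between the two sets would be visible. This stands. A reader might infer that blinding is judged in the FAS alone; the text does not support that.

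A reader might also infer that the plan will declare the blind broken or intact on the FAS result. It will not. There is no decision rule, the analysis sits under Other Analyses outside the testing hierarchy, and nothing depends on it. That the test is run in the FAS at all is itself an inference, though the natural one, because the test sentence names no set.

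Next, the FAS contrast has a use of its own. The primary analysis compares these same two groups, and a difference in belief between them bears on expectation bias in that comparison. This stands in part. Such a difference is worth describing, but it answers another question and should not be labelled a test of the trehalose blind.

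Last, the sizes rest on assumed inputs. The documents give neither the number of shared placebo participants nor any guess rate, the Exit Questionnaire itself is not in them, and pooling is harmless when guess rates agree. All true. But nothing in the documents gives grounds to expect equal guess rates across different products and routes, and the test's validity should not depend on that.

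What remains is that two tests of one question may disagree, and the SAP does not say which one assesses the trehalose blind.

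**Conclusion.** The point holds as a minor matter of analysis choice and labelling. On the natural reading of section 6.7.5, Fisher's test and the confidence bounds are produced in both sets. The FAS version confounds arm with regimen and is not a valid test of the trehalose blind; the ERO version is.

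Under the stated assumptions the FAS test can err in both directions. With an intact blind it rejects in 15-48% (80 shared) or 28-79% (160 shared) of trials, against 4% in the ERO. With a broken blind it detects the problem in 31-51% or 17-41%, against 90%. These ranges apply only if shared placebo guess at the assumed rates, which differ from those of RGE placebo.

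The documents do not support reading this as a plan without a sound blinding assessment, or as a threat to the primary analysis. Nor do they establish that most placebo guesses in the FAS come from other regimens: that is likely, but requires more than 40 shared placebo respondents, a count that is not given.

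**What to change.** In SAP section 6.7.5, state that the Fisher's exact tests, differences and confidence bounds that assess blinding are done in the ERO, separately for participants and for site investigators, among all respondents and among those at least somewhat sure.

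Tabulate FAS placebo guesses by regimen. Any FAS difference between active and placebo should be descriptive and labelled as imbalance of belief in the primary-analysis set, not as a test of the trehalose blind.

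The cost is about one sentence of SAP wording and a by-regimen layout for one table. It uses a set that the section already names and changes no data collection. The small downside is that a FAS p-value is no longer reported as a blinding test.

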6.7.6 Impact of COVID-19 Pandemic

The proportions of planned assessments missed due to COVID-19 restrictions or disruptions will be summarized by treatment group, visit, and type of assessment in the FAS and ERO . Protocol deviations that resulted from COVID-19 restrictions or disruptions will be summarized by treatment group and type of deviation in the FAS and ERO and listed.

7. Validation

7.1 Primary Efficacy Analysis

Validation of the primary efficacy analysis is as specified in the M-SAP. In addition, Seelos will perform a replication of the primary efficacy results (including any sensitivity analyses) using an independent programmer.

7.2 Secondary, Exploratory, and Safety Analyses

Validation of secondary, exploratory, and safety analyses are the same as specified in the M-SAP with the following clarifications.

Three levels of validation will be used:

- Level 1: Replication of results by an independent programmer.
- Level 2: When a macro is used to generate multiple results, one result will be replicated by an independent programmer.
- Level 3: Log files will be inspected for error messages and / or relevant warnings.

A separate validation document will be created in which the validation level applied for each analysis is specified. The level of validation will be based on whether the result is considered core or supplementary. Core results will be based on validation level 1 or level 2. Supplementary results will be based on level 3 validation. Examples of core results include primary and key secondary efficacy and safety endpoints. Examples of supplementary results include exploratory efficacy endpoints, selected sensitivity analyses, and selected sensitivity analysis data sets for secondary efficacy endpoints. Any analyses that fail due to small sample size or lack of convergence will be omitted with comment rather than programmed separately to find a post-hoc, work-around solution.

8. References

The following references are cited in addition to those specified in the M-SAP:

- Rubin DB. Causal inference through potential outcomes and principal stratification: Application to studies with "censoring" due to death. Statist. Sci. 2006 Aug;21(3):299-309.

